5.2 Phase 2 Study

At the completion of the phase 1b study, the safety of the PAC-1 and entrectinib combination will be assessed and recommendations will be provided regarding whether to proceed to the phase 2 portion of the study. The sponsor-investigator, Vanquish Oncology, and Genentech will review the DSMB recommendations, and make a decision regarding whether this combination is safe to warrant further study of this combination in a phase 2 study.

The primary objective of the Phase II trial is to determine the activity of the combination of PAC-1 and entrectinib for subjects with uveal melanoma as assessed by PFS at 3 months. Entrectinib, 600 mg orally, will be given Days 1 to Day 28 of each cycle and the recommended phase 2 dose (RP2D) of PAC-1 (PO) will be given on Days 1 to Day 21. Each cycle is 28 days. Treatment will continue until disease progression (based on RECIST 1.1 criteria), unacceptable toxicity, subject withdrawal of informed consent, or subject death either from progression of disease, the therapy itself, or from other causes. Subjects who voluntarily withdrew from study treatment, have progressive disease, or unacceptable toxicities will be followed for survival every 2 months for 12 months from start of study treatment, then every 3 months for up to 24 months.

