The primary objective of the Phase 2 Study is to estimate 3 month progression-free survival (PFS) using RECIST v1.1 in subjects with metastatic uveal melanoma.

Phase II

Entrectinib dosed at 600 mg once daily; PAC-1 dosed once daily at RP2D from Phase 1b study.

ABBREVIATIONS

Abbreviation	Definition
AE	adverse event
ANC	absolute neutrophil count
ALK	anaplastic lymphoma kinase
ALT	alanine aminotransferase
ASCO	American Society of Clinical Oncology
AST	aspartate aminotransferase
BUN	blood urea nitrogen
CBC	complete blood count
cm	centimeter
CMP	comprehensive metabolic panel
CNS	central nervous system
CR	complete response
CT	computed tomography
CTCAE	(NCI) Common Terminology Criteria for Adverse Events
CTEP	Cancer Therapy Evaluation Program
CYP	cytochrome P450
dL	deciliter
DOOR	duration of response
ECG	electrocardiogram
ECOG	Eastern Cooperative Oncology Group
ERK	extracellular signal-regulated kinase
FDA	Food and Drug Administration
FDAAA	Food and Drug Administration Amendments Act
FDAMA	Food and Drug Administration Modernization Act
GFR	glomerular filtration rate
h	hour
Hgb	hemoglobin
IB	Investigator's Brochure
IND	Investigational New Drug
IRB	institutional review board
kg	kilogram
lbs	pounds
LDH	lactic dehydrogenase
mg	milligram
min	minute
mL	milliliter
mm ³	cubic millimeters

MRI	magnetic resonance imaging
MTD	maximum tolerated dose
NSCLC	non-small cell lung cancer
NTRK	neurotrophic tyrosine kinase
ORR	overall response rate
OS	overall survival
PAC-1	first procaspase-activating compound
PFS	progression-free survival
PK	pharmacokinetics
PR	partial response
PT	prothrombin time
PTT	partial thromboplastin time
RECIST	Response Evaluation Criteria in Solid Tumor
ROS1	ROS proto-oncogene 1
SAE	serious adverse event
SDEA	Safety Data Exchange Agreement
TKI	tyrosine kinase inhibitor
Trk	tropomyosin-related kinase
ULN	upper limit of normal
US	United States
WHO	World Health Organization
WOCP	women of childbearing potential
wt	weight

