5.1.1 Dose Escalation Rules and MTD Definition

- Three subjects will initially be enrolled at dose level 1. If none of the 3 subjects experience a dose limiting toxicity (DLT) during the first cycle of therapy, three subjects will be enrolled at dose level 2. If all subjects in dose level 2 complete the first cycle of therapy without DLT, 3 more subjects will be enrolled into dose level 2 to ensure only 0-1 of 6 subjects have a DLT. There will be no further escalation beyond dose level 2.
- Alternatively, if 1 of the first 3 subjects within a dose level cohort experiences a DLT, the cohort will be expanded to 6 subjects. If this happens within dose level 1 and only 1 of the total 6 subjects in dose level 1 experience DLT, the study will proceed to dose level 2. If 2 or more of 6 subjects in a cohort experience DLTs, or 2 subjects within a cohort of 3 subjects experience DLT during the first cycle of therapy (>33% of subjects experiencing DLT), the MTD is exceeded. If this occurs at dose level 1, additional subjects will be accrued to dose level -1. If this occurs at dose level 2, 3 additional subjects will be

enrolled into dose level 1, unless there have been 6 subjects already enrolled into dose level 1.

- The MTD of PAC-1 in combination with entrectinib is the highest tested dose of PAC-1 combined with entrectinib with DLT rate of less than 33% in the first cycle of therapy (i.e., ≤ 1 out of 6 subjects with DLT). That dose will be recommended for the Phase 2 study.
- At the discretion of the sponsor-investigator, a lower Phase 2 dose may be recommended if other toxicity emerges during the Phase 1b study which does not meet DLT criteria but limits the dose that can be administered cumulatively.

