10.2.5 Dosage and Administration

An entrectinib dose of 600 mg will be tested in the Phase 1b and Phase 2 studies. Capsules are taken with water and food.

Entrectinib will be supplied as 200 and 400 mg capsules. Entrectinib capsules are packaged in white high-density polyethylene bottles with child resistant closures and a tamper-proof heat induction seal. Capsules will be distributed to patients by licensed pharmacist according to the clinical protocol and the separate Investigator Brochure.

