12.5 Data Analysis Plans

12.5.1 Analysis Plans for Primary Endpoint

Phase Ib Analysis of Primary Endpoint

The primary endpoint is determination of the MTD of PAC-1 in combination with entrectinib. The MTD will be defined as the highest explored dose of PAC-1 combined with 600 mg of entrectinib at which ≤ 1 out of 6 subjects have experienced a DLT within the first cycle of therapy. That dose will be recommended for the Phase 2 study (i.e., will be declared the RP2D). At the discretion of the sponsor-investigator, a lower Phase 2 dose may be recommended if other toxicity emerges during the Phase Ib study which does not meet DLT criteria but limits the dose that can be administered cumulatively.

Phase II Analysis of Primary Endpoint

The primary endpoint is determination of the activity of the combination of PAC-1 and entrectinib for treatment of metastatic uveal melanoma, as assessed by 3 months PFS based on RECIST v1.1. Median PFS times will be computed with associated 95% confidence intervals. Kaplan-Meier curves will be plotted.

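### If only Dose Level -1 (PAC-1 625 mg with entrectinib 400 mg) clears in Phase 1b, the protocol gives conflicting answers on the Phase 2 dose

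*Combined protocol and SAP*

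**What the plan says.** The dose table in Section 5.1 lists three PAC-1/entrectinib pairs in mg per day: Level -1 is 625/400, Level 1 (the start) is 625/600, and Level 2 is 750/600. Level -1 is the only level that lowers entrectinib.

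The texts that decide what follows a failed Level 1 are these:

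- **Section 5.1.1, branch:** "If this occurs at dose level 1, additional subjects will be accrued to dose level -1".
- **Section 5.1.1, MTD:** the "highest tested dose of PAC-1 combined with entrectinib with DLT rate of less than 33% in the first cycle of therapy", which is the dose recommended for Phase 2. It sets no 600 mg condition. Section 2.4.1 uses the same definition.
- **Section 12.5.1, MTD and RP2D:** the "highest explored dose of PAC-1 combined with 600 mg of entrectinib" with at most 1 of 6 subjects having a DLT. That dose is declared the RP2D.
- **Section 5.2:** "Entrectinib, 600 mg orally, will be given Days 1 to Day 28 of each cycle", with PAC-1 at the RP2D.
- **Phase 2 schema:** "Entrectinib dosed at 600 mg once daily; PAC-1 dosed once daily at RP2D from Phase 1b study".
- **Section 10.2.5:** "An entrectinib dose of 600 mg will be tested in the Phase 1b and Phase 2 studies".
- **Section 5.3.2:** the PAC-1 dose found to be the MTD is the one taken in Phase 2.

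Section 12.3.1 plans 9 to 12 subjects in Phase 1b. It then carries 6 subjects from the MTD level into Phase 2 and adds 29, for 35.

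**The concern.** The de-escalation step changes entrectinib, but the Phase 2 dosing text lets only PAC-1 vary. After a failed Level 1 and a cleared Level -1, a literal reader of the Phase 2 sections would return to the combination that had just exceeded the toxicity limit. A literal reader of Section 12.5.1 would conclude that there is no RP2D.

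Two things are at stake. The first is the starting dose of 29 patients, in a branch that the design itself specifies. The second is the primary analysis. Six subjects from the MTD level count towards the 35, so following the fixed 600 mg text would pool 6 subjects started on entrectinib 400 mg with 29 started on 600 mg in the 3-month PFS estimate.

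**Working it through.** **Tracing the branch.** Suppose Level 1 (625/600) exceeds the MTD and Level -1 (625/400) has at most 1 of 6 subjects with a DLT.

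| Text | Phase 2 dose it yields |
|---|---|
| 5.1.1 and 2.4.1 | 625/400: it is the only tested pair meeting the DLT limit, and 625/600 is disqualified |
| 12.5.1 | None: no 600 mg pair cleared, so there is no MTD or RP2D. Whether Phase 2 then stays closed is not stated |
| 5.1.1 and 5.3.2 for PAC-1, with 5.2 and the schema for entrectinib | 625/600, the rejected pair |

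**Clauses that might settle it.** The discretion in Section 5.1.1 says "a lower Phase 2 dose may be recommended if other toxicity emerges during the Phase 1b study which does not meet DLT criteria". Here the trigger is DLTs, so it does not apply. The review in Section 5.2 decides whether to proceed and has no rule for choosing a dose. The 400 mg step in Section 6.3.2 is an individual reduction from a 600 mg start.

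**Does the branch fit the planned enrolment?** The plan's own figures reproduce: 6 + 29 = 35 for Phase 2, and 3 + 6 + 29 = 38 in total. On the direct path, Level 1 stops after 3 or 6 subjects and Level -1 takes 6. That is 3 + 6 = 9 or 6 + 6 = 12, the 9 to 12 in Section 12.3.1. A later path, in which Level 2 fails and Level 1 then fails on expansion, would need 3 + 3 + 3 + 6 = 15 to 3 + 6 + 3 + 6 = 18. That exceeds the maximum and is not counted below.

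**How likely is the branch?** The documents give no DLT rate, so the true rates are assumed: p at Level 1 and q at Level -1.

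- P(Level 1 rejected at first evaluation) = P(at least 2 of 3) + P(exactly 1 of 3) × P(at least 1 of the next 3).
  - p = 0.10: 0.028 + 0.243 × 0.271 = 0.028 + 0.066 = 0.094
  - p = 0.20: 0.104 + 0.384 × 0.488 = 0.104 + 0.187 = 0.291
  - p = 0.30: 0.216 + 0.441 × 0.657 = 0.216 + 0.290 = 0.506
- P(Level -1 clears) = P(at most 1 of 6) = (1−q)^6 + 6q(1−q)^5.
- P(conflict arises) is the product of the two.

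| p | Level 1 rejected | Clears, q = p | Joint, q = p | Clears, q = p/2 | Joint, q = p/2 |
|---|---|---|---|---|---|
| 0.10 | 0.094 | 0.886 | 0.083 | 0.967 | 0.091 |
| 0.20 | 0.291 | 0.655 | 0.191 | 0.886 | 0.258 |
| 0.30 | 0.506 | 0.420 | 0.212 | 0.776 | 0.393 |

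**The case against.** The strongest reply is that the rejected pair appears only by combining sections. Section 12.5.1 is where the RP2D is defined, and Section 5.2 and the schema take PAC-1 from that RP2D. If no 600 mg pair clears, there is no RP2D and those sections have no PAC-1 dose to give. Read on their own, these three texts agree, and the outcome is no Phase 2. This does not remove the third answer. Section 5.3.2 carries the PAC-1 MTD dose into Phase 2 without reference to the RP2D, and Section 5.1.1 sends its MTD to Phase 2 directly. Following 5.1.1, 5.3.2 and 5.2 literally gives 625/600. Even without that answer, 625/400 and no Phase 2 would still be in conflict.

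Several other points stand in whole or part:

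- Section 10.2.5 states 600 mg for Phase 1b as well, so it reads as a default dose and is weak evidence of conflict. The same holds for Section 5.3.1 and the cycle tables in Section 5.1, which also omit Level -1. The conflict does not depend on any of them.
- The dose-table footnote and Section 12.3.1 speak of the MTD cohort or level without excluding Level -1, which favours 625/400. That is an inference, and Section 12.5.1 says otherwise.
- The review before Phase 2 would probably notice that 625/600 had failed. It would still have to choose between 625/400 and not opening Phase 2 without a written rule.
- The match to 9 to 12 subjects shows that the branch fits the plan, not that it was budgeted. Section 12.3 builds its count from Levels 1 and 2.

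**Conclusion.** The concern holds. In one branch that Section 5.1.1 prescribes, the stated rules give 625/400, no RP2D, or the rejected 625/600, and nothing in the document ranks them. This is a contradiction between dosing rules that bears on safety, so it should be fixed.

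Its reach is limited. It arises only if Level 1 fails and Level -1 clears; otherwise every text agrees on 600 mg. The probabilities, 8% to 21% with equal DLT rates and 9% to 39% with half the rate at Level -1, rest on assumed Level 1 rates of 10% to 30%. They illustrate that the branch is not remote and do not determine how serious the contradiction is. They stop short of the safety review, so they do not measure harm. The Phase 2 sample-size calculation is unaffected.

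**What to change.** Define the MTD and RP2D in Sections 2.4.1, 5.1.1 and 12.5.1 as a PAC-1/entrectinib dose pair. Replace the fixed 600 mg in the Phase 2 schema, the Section 5.1 cycle tables and Sections 5.2, 5.3.1 and 10.2.5 with the entrectinib dose of the assigned level or of the RP2D pair. Add a 400 mg starting column to Section 6.3.2, which now lists only 600, 400 and 200 mg and allows two reductions.

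Alternatively, state that Phase 2 will not open if no pair with entrectinib 600 mg clears. The choice is clinical and belongs to the sponsor. It should be written down before Level 1 results force it.

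Either option needs only amendment wording, although adopting 625/400 would be a real change to the Phase 2 regimen. With 625/400 as the RP2D, enrolment is 3 + 6 + 29 = 38 if Level 1 stops after 3 subjects, which is the stated total, or 6 + 6 + 29 = 41 if it stops after 6. The current rules already reach 41 when Level 1 is expanded to 6 before Level 2 clears.

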5.3 Administration of Study Drugs

Criteria for the initiation of a new cycle of treatment can be found in Section 6.1. All tablets are to be ingested as dispensed by research team (e.g. tablets may not be broken or crushed by subject); patients who have difficulty swallowing tablets will be excluded from the study. If vomiting occurs during the course of treatment, no re-dosing of the patient is allowed before the next scheduled dose. Missed doses will not be made up. A window of \pm 3 days may be applied to all study visits to accommodate observed holidays, inclement weather, scheduling conflicts etc. Date and time of each drug administration should be clearly documented in subject's chart and electronic case report forms (eCRFs).

Patients will keep a drug diary to record each dose of the study drugs and time of day when administered, and any side effects they are experiencing. Research staff will record information from the diaries, discuss any concerns the patient has regarding the treatment, and will also collect any unused medication during these visits. Patients will be closely monitored for toxicities and CTCAE v5 will be used to assess toxicities.

5.3.1 Entrectinib

Entrectinib (PO) will be dosed at 600 mg daily in the evening on Days 1-28 of each 28 day cycle (for exception in Cycle 1, see below). During Cycle 1 for each dose cohort, subjects will be instructed to administer their daily dose at the same approximate time (+/- 1 hour) each evening. The study drug will be administered in the evening. Patients will be instructed to take each oral dose of entrectinib with 8 ounces of water (1 cup, 240 mL) and with food.

Entrectinib therapy will be withheld on Days 1 and 2 and initiated during Cycle 1 on Day 3 to continue for the remainder of the cycle. Administration of entrectinib on Days 3 and 21 of Cycle 1 will occur in the morning. Entrectinib administration will occur 1 hour before PAC-1 on Day 21. Information on the time and number of entrectinib doses received for the 96 hours prior to the dose on Day 21 will be obtained from subjects.

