5 OVERALL DESIGN AND TREATMENT PLAN

5.1 Phase 1b Dose Escalation Plan

This Phase Ib dose escalation study will evaluate entrectinib in combination with PAC-1 in subjects with metastatic uveal melanoma. Entrectinib will be taken orally on Days 1-28 of each 28 day cycle and PAC-1 will be taken orally on Days 1-21 of each 28-day cycle (see exception for Cycle 1 below), and response to treatment will be evaluated after every 2 cycles. Treatment will continue until disease progression (based on RECIST 1.1 criteria), unacceptable toxicity, subject withdrawal of informed consent, or subject death either from progression of disease, the therapy itself, or from other causes. Subjects who withdrew from study treatment, have progressive disease, or unacceptable toxicities will be followed for survival every 2 months for 12 months from start of study treatment, then every 3 months for up to 24 months.

Pharmacokinetic (PK) and pharmacodynamic (PD) assay for PAC-1 will be performed during Days 1 and 21 of Cycle 1. PAC-1 will be given on Day 1 of Cycle 1, withheld on Day 2 and Day 3 of Cycle 1 then reinitiated on Day 4 of Cycle 1 to continue to Day 21 of the 28-day cycle. For

each successive cycle, PAC-1 therapy will be initiated on Day 1 and continue to Day 21 of the 28-day cycle.

Pharmacokinetic and pharmacodynamic assay for entrectinib will be performed during Days 3 and 21 of Cycle 1. Entrectinib therapy will be withheld on Day 1 and Day 2 of Cycle 1, initiated on Day 3 of Cycle 1 and continue for the remainder of the cycle. For each successive cycle, entrectinib will be initiated on Day 1 and continue for the remainder of the 28 day cycle.

Cycle 1 of Treatment (Cycle = 28 Days)

Drug	Dose	Route	Cycle 1 Frequency
PAC-1	TBD	Orally	Day 1 then Day 4 to Day 21; HELD Day 2 and Day 3
Entrectinib	600 mg		Day 3 to Day 28; HELD Day 1 and Day 2

Cycle 2 and Subsequent (Cycle = 28 Days)

Drug	Dose	Route	Frequency
PAC-1	TBD	Orally	Day 1 to Day 21
Entrectinib	600 mg		Day 1 to Day 28

Study Treatment Dose Levels

Dose Level*	PAC-1 Dose (mg, orally)	Entrectinib (mg, orally)	# of Subjects [^]
-1	625 daily	400 daily	3-6
1 (starting)	625 daily	600 daily	3-6
2	750 daily	600 daily	3-6

*Pharmacokinetics analysis will be performed at both dose levels during Cycle 1.

[^]MTD cohort will be initially expanded to 6 patients, and if no DLT move to Phase 2 study.

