8.1 Peripheral Blood Samples

8.1.1 Plasma for Pharmacokinetics and Pharmacodynamics

In phase 1b, the pharmacokinetics (PK) and pharmacodynamics (PD) of PAC-1 will be assessed following doses administered on Days 1 and 21 of the first cycle. In phase 1b, the PK and PD of entrectinib will be assessed following the dose administered on Days 3 and 21 of the first cycle. Entrectinib will be withheld on Days 1 and 2 to allow assessment of PAC-1 PK when administered as single agent. PAC-1 will be withheld on Days 2 and 3 to allow assessment of entrectinib PK when administered as single agent on Day 3. PKs of both drugs will be assessed on Day 21 to determine effects of repeated dosing or combining of the two drugs. The PK and PD analyses will occur with each dose level.

Administration of PAC-1 on Days 1 and 21 and entrectinib on Days 3 and 21 of Cycle 1 will occur in the morning. Entrectinib administration will occur 1 hour before PAC-1 on Day 21. The dose timing on this day is being specified to accommodate a sampling schedule that minimizes the number of blood draws needed from the patient. Information on the time and number of PAC-1 and entrectinib doses received for the 96 hours prior to the dose on Day 21 will be obtained from subjects. Patients will not receive their PAC-1 dose on Days 2 and 3 of Cycle 1. The doses on these days are being held in order to accurately define the absorption and metabolism of entrectinib when administered as a single agent on Day 3. Likewise, patients will not receive their entrectinib dose on Days 1 and 2 of Cycle 1. The doses on these days are being held in order to accurately define the absorption and metabolism of PAC-1 when administered as a single agent on Day 1. Actual and nominal sample collection times will be recorded on the case report forms and sample tubes.

Sample collections will occur in the mornings on Day 1 (PAC-1 only), Day 3 (entrectinib only), and Day 21 (PAC-1 and entrectinib) of the first cycle.

- Day 1, Cycle 1: Subjects receive only PAC-1.
 - Blood samples are collected immediately prior to oral ingestion of PAC-1 and at the following time points after ingestion: 0.5, 1, 2, 3, 4, 6, 7, and 24 hours.
- Day 3, Cycle 1: Subjects receive only entrectinib.
 - Blood samples are collected immediately prior to oral ingestion of entrectinib and at the following time points after ingestion: 0.5, 1, 2, 3, 4, 6, 7, and 24 hours.
- Day 21, Cycle 1: Subjects receive both PAC-1 and entrectinib.

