8.1.1.1 Pharmacokinetic Analysis

Non-compartment analysis: Non-compartmental analysis of the PAC-1 plasma concentration-time data following doses on Days 1 and 21 for Cycle 1 for each dose level. Also on Days 3 and 21 of Cycle 1, entrectinib plasma concentration data will be performed using WinNonlin 6.3 (Pharsight, St Louis, MO) for subjects in whom complete PK profiles are obtained.

Pharmacokinetic parameters to be estimated following each dose include: 1). area under the PAC-1 plasma concentration-time curve from time 0 to 24 hours (AUC_{0-24}) for days 1 and 21, 2) area under the entrectinib plasma concentration-time curve from 0 to 24 hours (AUC_{0-24}) for Days 3 and 21, 3). area under the PAC-1 plasma concentration-time curves from time 0 to infinity ($AUC_{0-\infty}$) on Day 1 only, 4). area under the entrectinib plasma concentration-time curves from time 0 to infinity ($AUC_{0-\infty}$) on Day 3 only, maximum PAC-1 and entrectinib plasma concentrations (C_{max}), 5). terminal elimination rate constant for both drugs (λ_z), and 6). oral clearance (CL/F) for both drugs.

Statistical Analysis: The influence of multiple dosing (e.g., PAC-1 Day 1 $AUC_{0-\infty}$ vs. Day 21 AUC_{0-24} and entrectinib Day 3 $AUC_{0-\infty}$ vs. Day 21 AUC_{0-24}), concurrent administration of PAC-1 and dose on the pharmacokinetics of entrectinib (e.g., Day 3 $AUC_{0-\infty}$ vs. Day 21 AUC_{0-24}), and concurrent administration of entrectinib and dose on the pharmacokinetics of PAC-1 (e.g., Day 1 $AUC_{0-\infty}$ vs. Day 21 AUC_{0-24}), will be evaluated using a generalized linear models approach. PAC-1 AUC_{0-24} , $AUC_{0-\infty}$, C_{max} and CL/F will be log transformed before statistical analysis. Entrectinib AUC_{0-24} , $AUC_{0-\infty}$, C_{max} and CL/F will be log transformed before statistical analysis. Geometric means will be calculated for the parameters on each study day. The 90% confidence intervals for the geometric mean ratios will be constructed for every comparison.

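### Evening entrectinib dosing up to Day 20 and a morning dose on Day 21 mean that the planned Day 21/Day 3 AUC ratio does not equal 1 when nothing has changed

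*Combined protocol and SAP*

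**What the plan says.** Section 5.3.1 sets the routine: "Entrectinib (PO) will be dosed at 600 mg daily in the evening on Days 1-28 of each 28 day cycle". For Cycle 1 it adds that "subjects will be instructed to administer their daily dose at the same approximate time (+/- 1 hour) each evening". The exception is the PK days: "Administration of entrectinib on Days 3 and 21 of Cycle 1 will occur in the morning". The Cycle 1 table in Section 5.1 gives the entrectinib schedule as "Day 3 to Day 28; HELD Day 1 and Day 2", so no dose between Day 3 and Day 28 is held, and no passage moves the Day 20 dose.

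Section 8.1.1 explains the Day 21 timing by the wish to limit blood draws and does not discuss the interval since the previous dose. It does require a record of "Information on the time and number of PAC-1 and entrectinib doses received for the 96 hours prior to the dose on Day 21".

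Section 8.1.1.1 specifies non-compartmental analysis, then a generalized linear model on log-transformed parameters, with geometric mean ratios and 90% confidence intervals. "The influence of multiple dosing" on entrectinib and the effect of concurrent PAC-1 are both judged from Day 3 AUC0-infinity against Day 21 AUC0-24. The section gives no role to the recorded dose times.

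PAC-1 is taken every morning (Section 5.3.2), so its Day 20 to Day 21 interval stays near 24 hours.

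**The concern.** Single-dose AUC0-infinity equals AUC0-24 at steady state, with linear kinetics and unchanged clearance, only when the measured interval is a regular one. If the Day 21 dose comes about 12 hours after the Day 20 dose, the Day 21 window also contains the 12-to-24-hour part of that earlier dose, which a regular interval would not. Day 3 is the first entrectinib dose and has no carry-over, so nothing offsets the excess.

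The shift comes from the schedule and applies to every subject who follows it. The geometric mean ratio would centre above 1 with no effect present, and more subjects would not remove this. A reader of the results would take the excess for accumulation or for inhibition of entrectinib clearance by PAC-1. Section 2.3 lists entrectinib PK after repeated dosing and with PAC-1 as an exploratory objective.

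**Working it through.** The documents state no figure to reproduce, so the check is what the planned ratio would be if nothing changed.

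**Inputs from the protocol.** Evening dosing, with mornings on Days 3 and 21 (5.3.1); no hold after Day 2 (5.1); Day 3 AUC0-infinity against Day 21 AUC0-24 (8.1.1.1).

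**Assumptions.** Linear one-compartment kinetics; unchanged clearance and bioavailability; a 12-hour gap; half-lives of 4 to 60 hours. Half-life, absorption rate and clock times are not in the documents.

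**Step 1: formula.** Let k = ln 2 / half-life and g = hours between the Day 20 and Day 21 doses. Express areas as shares of single-dose AUC0-infinity.
- The Day 21 dose's own area over 24 h is 1 − exp(−24k).
- Carry-over from earlier doses over the same 24 h, at steady state, is exp(−gk).
- The no-effect ratio is R(g) = 1 − exp(−24k) + exp(−gk).

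At g = 24, R = 1. At g = 12, with x = exp(−12k), R = 1 + x − x².

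**Step 2: numbers, bolus input, g = 12.**

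| Half-life (h) | x | R |
|---|---|---|
| 4 | 0.125 | 1.109 |
| 8 | 0.354 | 1.229 |
| 12 | 0.500 | 1.250 |
| 20 | 0.660 | 1.224 |
| 40 | 0.812 | 1.152 |
| 60 | 0.871 | 1.113 |

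The maximum is 1.25, at x = 0.5.

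**Step 3: sensitivity to the gap.** At a 20 h half-life, R is 1.27 (10 h gap), 1.22 (12 h), 1.18 (14 h) and 1.00 (24 h).

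**Step 4: actual schedule.** Doses were placed on Day 3 morning, Days 4 to 20 evening and Day 21 morning, without assuming steady state.
- Bolus input agrees with Step 2 (1.107 instead of 1.113 at 60 h).
- For half-lives of 4 to 60 h, first-order absorption gives 1.11 to 1.27 at 1.0 per hour and 1.11 to 1.31 at 0.3 per hour.
- At very long half-lives Day 21 is short of steady state, which offsets the excess: 1.07 at 80 h and 0.985 at 120 h. Even at 120 h the short gap raises the ratio, since a 24 h gap would give 0.928.
- If the Day 20 evening dose were skipped (about a 36 h gap), the ratio would be about 0.83 to 0.99 for half-lives of 3 to 120 h with absorption at 0.3 per hour.

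**Step 5: which correction works.** Subtract the carry-over, Cpre/λz × (1 − exp(−24λz)), from Day 21 AUC0-24 and compare with Day 3 AUC0-24. In the bolus model this gives (1 + x − x² − x)/(1 − x²) = 1. If the Day 21 AUC is instead extrapolated to infinity from the observed C24, the tail still holds carry-over of x³/(1 − x²): 0.17 at a 12 h half-life, 0.51 at 20 h and 1.57 at 40 h. The last two give ratios of about 1.5 and 2.6, further from 1 than the uncorrected 1.22 and 1.15.

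**The case against.** **The gap and its size are inferred.** This is true. The protocol gives only evening and morning, and no half-life. The existence of a shortened interval follows from the text; its size does not.

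**The net direction is not settled.** A reader might infer that the reported ratio will certainly be too high. The documents do not support that. Section 5.3.1 has entrectinib taken with food and, on Day 21, one hour before PAC-1. Section 5.3.2 requires nothing by mouth except water and prescribed medications for two hours before PAC-1. Both cannot be followed on Day 21 as written, so fed state may differ between Day 3 and Day 21 and move the ratio either way. A skipped Day 20 dose would pull it below 1. What is established is an upward component due to the dose interval.

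**The inputs for a correction are collected, and the AUC contrasts are introduced as examples.** This is also true: diaries, case report forms and the 96-hour history would support a correction. However, none is planned, and the comparison that is named gives a shifted ratio when followed.

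**The consequence is small.** The endpoint is exploratory, limited to Phase 1b (9 to 12 subjects by Section 12.3.1), and analysed only if funding arrives (Section 8). Assuming a within-subject CV of 30 to 40%, which the documents do not give, the 90% interval would extend by a factor of about 1.24 (12 subjects, 30%) to 1.40 (9 subjects, 40%). The shift is then similar to or smaller than the imprecision. That limits the priority of the point, but a wide interval centred in the wrong place is still in the wrong place. It also stands that one Day 3 versus Day 21 contrast cannot separate repeated dosing from PAC-1 co-administration, even after correction.

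**Conclusion.** The entrectinib comparison in Section 8.1.1.1 is wrong as written and should be changed. If the stated schedule is followed, the no-effect ratio is not 1. The dose interval alone puts it at about 1.11 to 1.25 with bolus input, and up to about 1.31 with slow absorption, given a 12-hour gap, linear one-compartment kinetics, unchanged clearance and half-lives of 4 to 60 hours.

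A reader might infer that this undermines the dose decision or the efficacy result. It does not: MTD rests on DLT counts, the Phase 2 endpoint is 3-month PFS, and neither they nor the sample size use these AUCs. The PAC-1 comparison is not affected by this mechanism.

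**What to change.** In Section 8.1.1.1:
- Make the main entrectinib Day 21 versus Day 3 comparison a compartmental (model-based) analysis that uses the recorded dose times and the 96-hour dose history. Report the uncorrected non-compartmental ratio as a supplement.
- As a simple sensitivity analysis, subtract the carry-over estimated from the Day 21 pre-dose sample from Day 21 AUC0-24, and compare the result with Day 3 AUC0-24. Both are already planned parameters, and no tail is extrapolated. If AUC0-infinity is used on Day 21, C24 must be corrected for carry-over as well.
- Reconcile the food instruction in Section 5.3.1 with the fasting instruction in Section 5.3.2 for Day 21.

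The analysis changes need no new samples, only some extra PK work. The cost is dependence on model assumptions, or on a λz that is poorly supported: there is a single sample after the 7-hour draw, and a λz taken from the 7- and 24-hour samples can overcorrect when absorption is slow. The planned Day 3 AUC0-infinity is exposed too, since its extrapolated share, exp(−24k), would be 25% at a 12 h half-life, 44% at 20 h and 66% at 40 h. This is why the sensitivity analysis should stay within 24 hours.
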